# 11.4.2 Hand Eczema Severity Index (HECSI)

The HECSI is an instrument used in clinical trials to rate the severity of 6 clinical signs (erythema, infiltration/papulation, vesicles, fissures, scaling, and oedema) and the extent of the lesions on each of the 5 hand regions (fingertips, fingers [except fingertips], palm of hands, back of hands, and wrists) by use of standard scales (36).

For each hand region (total of both hands, e.g. 10 fingers), the investigator rates the average severity of each of the 6 clinical signs of hand eczema using a 4-point severity scale ranging from 0 (none/absent) to 3 (severe) (Panel 12). The investigator also rates the extent of the lesions by assessing82 the percentage of the hand regions these lesions occupy and converting it to a score based on a 5-point scale (the area score) (Panel 12). For each of the hand regions, the region score will be calculated by adding up the severity scores for the 6 clinical signs of

hand eczema and multiplying with the area score (Panel 13). The HECSI score equals the sum of the region scores and will range from 0 (lowest possible score) to 360 (highest possible score).

The HECSI will be assessed according to the schedule of trial procedures (Section 4). The assessment will be based on the condition of the disease at the time of evaluation and not in relation to the condition at a previous visit. New CHE lesions that occur on previously untreated areas will be included in the assessment.

Panel 12: HECSI severity score scale and area score scale

Severity score (SS) scale (based on both hands)					
0	None/absent				
1	Mild				
2	Moderate				
3	Severe				

Note: half-scores (0.5, 1.5, 2.5) are not allowed.

Area score (AS) scale (based on the affected area of both hands)					
0	0% affected area				
1	1% to 25% affected area				
2	26% to 50% affected area				
3	51% to 75% affected area				
4	76% to 100% affected area				

Note: half-scores (0.5, 1.5, 2.5, 3.5) are not allowed.

Panel 13: Calculation of the total HECSI score

Hand region	Erythema	Infiltration/ papulation	Vesicles	Fissures	Scaling	Oedema	Area score	Score
Fingertips	(SS+	SS+	SS+	SS+	SS+	SS)	× AS	
Fingers (except fingertips)	(SS +	SS+	SS+	SS+	SS+	SS)	× AS	
Palm of hands	(SS+	SS +	SS +	SS +	SS+	SS)	× AS	
Back of hands	(SS +	SS +	SS +	SS +	SS +	SS)	× AS	
Wrists	(SS+	SS+	SS +	SS +	SS+	SS)	× AS	
	(range 0-360)							

**Abbreviations:** AS = area score; HECSI = Hand Eczema Severity Index; SS = severity score.

Page 73 of 157

## 11.4.3 Patient-reported outcomes (efficacy)

## 11.4.3.1 Overview

Each subject must make individual assessments relating to their perception of their disease independently of the investigator and trial site staff.

The PRO HESD is considered an efficacy assessment in this trial. The HESD will be completed daily as an eDiary.

# 11.4.3.2 Hand Eczema Symptom Diary (HESD)

The HESD is an instrument used in the phase 2b trial with delgocitinib (LP0133-1273) and has been further revised for the current trial. The HESD is a -item PRO instrument designed to assess severity of CHE signs and symptoms. Subjects will assess the worst severity of individual signs and symptoms of CHE (CCI) over the past 24 hours using an 11-point numeric rating scale with anchors of 0 = 'no (symptom)' and 10 = 'severe (symptom)'. The HESD score is derived as an average of the items. Subjects will complete the HESD on a daily basis in an eDiary as outlined in Section 4.

## 11.5 Safety assessments

## 11.5.1 Vital signs

Vital signs (resting blood pressure, pulse, and body temperature) must be assessed according to the schedule of trial procedures (Section 4). Vital signs will be measured in a sitting position following at least 5 minutes of rest.

If an abnormal vital sign at screening is considered to be clinically significant by the investigator, it will be at the discretion of the investigator if the subject should be randomised into the trial (respecting exclusion criterion no. 20).

In case of abnormal findings, the vital sign measurement can be repeated approximately 15 minutes later to verify the first measurement. Should the repeated measurement result in a normal value, the measurement must be repeated once more. If the third measurement verifies the second (normal) value, the first measurement should be considered false and the second measurement should be recorded in the eCRF. If the third measurement confirms the first measurement (abnormal), the second measurement will be considered false and the first measurement should be recorded in the eCRF.

Page 74 of 157

## Reporting in eCRF

It will be recorded in the eCRF if vital signs were measured; if not, a reason should be provided. Vital signs (resting blood pressure, pulse, and body temperature) will be recorded in the eCRF. Clinically significant abnormal vital signs at the screening visit will be documented as medical history in the eCRF. At subsequent visits, any clinically significant deterioration of a pre-existing condition as well as any new clinically significant sign, symptom, or illness occurring after randomisation will be reported as an AE in accordance with Section 13.3.

# 11.5.2 Physical examination

A thorough physical examination of the subject including whole body inspection of the skin, auscultation of heart, lungs, and abdomen, palpation of the abdominal organs, and basic neurological status must be performed according to the schedule of trial procedures (Section 4). Presence of foot dermatitis will be documented. The investigator should perform the same examinations as in clinical practice as a minimum.

If an abnormal physical finding at screening is considered to be clinically significant by the investigator, it will be at the discretion of the investigator if the subject should be randomised into the trial (respecting exclusion criterion no. 20). In case only CHE is identified, the physical examination should be considered as normal.

### Reporting in eCRF

It will be recorded in the eCRF if a physical examination was performed and, if applicable, the investigator's evaluation ('normal', 'abnormal, not clinically significant', 'abnormal, clinically significant'). If a physical examination was not performed, a reason should be given.

Clinically significant abnormal findings at the screening visit will be documented as medical history in the eCRF. At subsequent visits, any clinically significant deterioration of a pre-existing condition as well as any new clinically significant sign, symptom, or illness occurring after randomisation will be reported as an AE in accordance with Section 13.3.

# 11.5.3 Electrocardiography

A single 12-lead resting digital ECG will be recorded after the subject has been supine for at least 5 minutes at the visits indicated in the schedule of trial procedures (Section 4).

A pre-evaluation of the ECGs will be performed by the investigators to evaluate immediate subject safety. At a minimum, the date of ECG recording will be documented in the source.

Page 75 of 157

The ECG data will be transferred to a central ECG service company for central evaluation. A cardiologist at the ECG service company will analyse and interpret the ECG data. The ECG service company will provide ECG evaluation reports to the trial sites.

The investigator must evaluate all abnormal ECG results ('clinically significant' or 'not clinically significant') and sign and date. The investigator has the final decision on the clinical significance of any ECG abnormalities. The investigator will document the review of the ECG results by signing the ECG report at the trial site or in an electronic portal hosted by the ECG vendor.

If an abnormal ECG finding at screening is considered to be clinically significant by the investigator, it will be at the discretion of the investigator if the subject should be randomised into the trial (respecting exclusion criterion no. 20).

The collection and transmission of ECG data will be described in a separate ECG manual. Test dummy transmissions will be undertaken prior to trial conduct to ensure that transmissions can be made, and that date and time settings are correctly set.

## Reporting in eCRF

It will be recorded in the eCRF if an ECG was performed and, if applicable, the investigator's assessment of ECG results ('normal', 'abnormal, not clinically significant', 'abnormal, clinically significant'). If an ECG was not performed, a reason should be given.

Clinically significant abnormal findings at the screening visit will be documented as medical history in the eCRF. At subsequent visits, any clinically significant deterioration of a pre-existing condition as well as any new clinically significant sign, symptom, or illness occurring after randomisation will be reported as an AE in accordance with Section 13.3.

## 11.5.4 Laboratory testing

#### 11.5.4.1 Overview

Blood and urine samples will be collected according to the schedule of trial procedures (Section 4).

The evaluations shown in Panel 14 will be performed by the central laboratory.

Page 76 of 157

Panel 14: Clinical laboratory tests performed by the central laboratory

Chemistry	Haematology
Sodium	Erythrocytes
Potassium	Haematocrit
Creatinine	Haemoglobin
Urea nitrogen	Erythrocyte mean corpuscular volume
Calcium	Erythrocyte mean corpuscular haemoglobin
Alkaline phosphatase	concentration
Aspartate aminotransferase	Leukocytes
Alanine aminotransferase	Neutrophils
Gamma glutamyl transferase	% neutrophils
Bilirubin 	Lymphocytes
Lactate dehydrogenase	% lymphocytes
Cholesterol	Monocytes
LDL cholesterol	% monocytes
HDL cholesterol	Eosinophils
Triglycerides	% eosinophils
Glucose (non-fasting)	Basophils
Albumin	% basophils
Protein	Thrombocytes
Urinalysis 	Serology 
Protein	Hepatitis B virus surface antigen
Glucose	Hepatitis C virus antibody
Ketones	HIV-1 antibody
Occult blood	HIV-2 antibody
Leukocytes	Immunoglobulin E
Nitrite	

- 1) If bilirubin is above upper limit of normal, direct and indirect bilirubin will also be measured.
- 2) Urine samples will be tested at the trial site (dipstick). It will be at the investigator's discretion to decide whether a urine sample should be sent to the central laboratory for microscopic examination (WBC; RBC; epithelial cells, squamous; epithelial cells, transitional; epithelial cells, renal tubular; hyaline casts; WBC casts; RBC casts; waxy casts; granular casts; calcium oxalate crystals; uric acid crystals; triphosphate crystals; yeast; and bacteria).
- 3) Measured at screening only.
- 4) In case additional analyses are needed to support the interpretation of the initial test results for hepatitis B, hepatitis C, or HIV, these will be performed by the central laboratory as applicable.

**Abbreviations:** HDL = high density lipoprotein; HIV = human immunodeficiency virus; LDL = low density lipoprotein; RBC = red blood cells; WBC = white blood cells.

Trial ID: LP0133-1402 Date: 20-Aug-2021

Page 77 of 157

Version: 4.0, Final

# 11.5.4.2 Investigator evaluation of laboratory samples

## **Central laboratory**

Chemistry, haematology, urinalysis (if applicable), and serology will be analysed by a central laboratory which will provide results to the trial sites. Laboratory parameters will be classified as 'low', 'normal', or 'high', depending on whether the value is below, within, or above the reference range, respectively. The investigator must evaluate all results outside the reference range ('clinically significant' or 'not clinically significant') and sign and date the evaluation. The signed and dated version will be filed with the investigator's trial documentation. In case of clinically significant abnormal results, appropriate action, as judged by the investigator, must be taken.

If a screening laboratory result is abnormal and clinically significant, it will be at the investigator's discretion to decide if the subject should be randomised into the trial (respecting exclusion criterion no. 20).

A laboratory manual will be provided to the trial sites specifying the procedures for collection, processing, storage, and shipment of samples, as well as laboratory contact information specific to this trial.

#### Tests performed at the trial site

Urine samples will be tested with a dipstick according to the schedule of trial procedures (Section 4). It will be at the investigator's discretion to decide whether a urine sample should be sent to the central laboratory for further analysis.

Women of childbearing potential will have a urine pregnancy test performed at the trial site at screening and at baseline prior to randomisation. The test will be repeated every 4 weeks as shown in the schedule of trial procedures in Section 4.

### Reporting in eCRF

At each visit, the site staff will record in the eCRF if a blood sample was taken. If not, a reason should be provided. The investigator's assessment of the results ('normal', 'abnormal, not clinically significant', 'abnormal, clinically significant') will be recorded in the eCRF.

It will be recorded in the eCRF if a urine dipstick test was performed and whether urinalysis is required for further assessment, as judged by the investigator. If so, a urine sample should be sent to the central laboratory. If the urine sample was not tested with a dipstick, a reason will be provided. The investigator's assessment of the urine dipstick results ('normal', 'abnormal') will be recorded in the eCRF. In case urinalysis is performed, the investigator's

assessment of the results ('normal', 'abnormal, not clinically significant', 'abnormal, clinically significant') will be recorded in the eCRF.

It will be recorded in the eCRF if the subject is a woman of childbearing potential and if a urine pregnancy test was performed. If not, a reason should be provided. Also, the date and the outcome of the urine pregnancy test will be recorded in the eCRF ('positive', 'negative').

Clinically significant abnormal laboratory results at the screening visit will be documented as medical history in the eCRF. At subsequent visits, any clinically significant deterioration of a pre-existing condition will be reported as an AE. Any new clinically significant sign, symptom, or illness occurring after randomisation will be reported as an AE in accordance with Section 13.3.

# 11.5.5 Assessment of local tolerability

Subjects and investigators will each provide an assessment of local tolerability according to the schedule of trial procedures (Section 4).

The subject will complete a weekly assessment of stinging/burning in connection with the IMP applications in the eDiary from Day 7 onwards. The subject will be asked to retrospectively assess the worst stinging/burning in connection with the IMP application during the last week. In addition, the subject will be asked by the investigator at the end-of-treatment/early termination visit to assess the local tolerability during the last week (see Section 4). The assessment will be done using the 4-point scale shown in Panel 15.

Panel 15: Subject assessment of local tolerability after IMP application

Grade (severity)	Stinging/burning
0 (none)	No stinging or burning.
1 (mild)	Slight warm, tingling sensation, not really bothersome.
2 (moderate)	Definitive warm, tingling sensation, that is somewhat bothersome.
3 (severe)	Hot, tingling/stinging sensation that has caused definite discomfort.

**Abbreviation:** IMP = investigational medicinal product.

The investigator will assess whether he/she suspects a local skin reaction related to application of the IMP. If the investigator suspects a local skin reaction related to application of the IMP, the skin reaction will be scored according to the Berger and Bowman scales in

Page 79 of 157

Panel 16. The scoring should only assess skin signs suspected to be related to application of the IMP and not signs or symptoms related to the subject's CHE.

Following scoring according to the Berger and Bowman scales, an IMP patch test will be performed to confirm a possible diagnosis of allergic contact dermatitis caused by the IMP, see procedure described in Section 11.5.5.1. The aetiology of the local skin reaction will be captured in the eCRF and the final diagnosis will be captured as an AE.

The subject's assessment of local tolerability may be reported as an AE at the discretion of the investigator, even if the investigator does not suspect a local skin reaction related to application of IMP (reporting of e.g. pain or stinging/burning by the subject).

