# **10.3** Early termination assessments

#### Permanent discontinuation of IMP

Subjects who permanently discontinue IMP for any reason will be asked to attend an early termination visit as soon as possible after last administration of IMP and return to the trial site for 2 additional visits as indicated below. See the schedule of trial procedures (Section 4) for data to be collected at these visits. The investigator will review any AEs which will be followed up according to Section 13.7, if the subject agrees.

Subjects who permanently discontinue IMP prior to Week 16 will be asked to attend the following visits:

- Early termination visit (as soon as possible after last administration of IMP).
- Safety follow-up visit (2 weeks after last administration of IMP, performed via phone, but can be a site visit if needed).
- Primary endpoint visit (16 weeks after randomisation).

Page 63 of 157

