# 11.3 eDiary assessments

At the screening visit, the subjects will receive an eDiary device and eDiary training. The eDiary will be open for entry from 4 pm until midnight. The subjects must start completing the HESD in the eDiary at least 1 week prior to baseline, but preferably from the date the subjects receive the eDiary. The HESD must be completed in the eDiary every evening until Week 16, regardless of IMP discontinuation. Treatment compliance (daily) and subject assessment of local tolerability (weekly) will be evaluated by the subject in the eDiary from baseline up to end of treatment/early termination. Compliance with the eDiary completion will be reviewed by the trial site staff throughout the trial.

Handout, training, and return of the eDiary is outlined in the schedule of trial procedures (Section 4). Return of the eDiary is not applicable for subjects who discontinue IMP and attend an early termination visit, but do not withdraw from the trial. These subjects will continue completing the eDiary until the primary endpoint visit at Week 16 and will return the eDiary at that visit. Subjects who will participate in the LTE trial must bring the eDiary to the Week 16 visit, so the trial site staff can set up the eDiary for the LTE trial. Daily completion of the eDiary will continue in the LTE trial.

The following assessments will be completed in the eDiary by the subjects in the listed order:

- Daily: HESD (see Section 11.4.3.2).
- Daily: treatment compliance (see Section 9.8.4).
- Weekly: subject assessment of local tolerability (see Section 11.5.5).

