# 14.3.12.4 Assessment of local tolerability

Assessment of local tolerability will be summarised by visit and treatment group.

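### The subject's early termination rating of stinging/burning covers the week before a visit with no maximum delay after the last application, so it can rate a week without IMP and still be tabulated as local tolerability

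*Combined protocol and SAP*

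**What the plan says.** Section 11.5.5 of the protocol has two subject ratings of stinging/burning.

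- **Weekly eDiary item:** "The subject will be asked to retrospectively assess the worst stinging/burning in connection with the IMP application during the last week".
- **Visit item, asked in addition:** "the subject will be asked by the investigator at the end-of-treatment/early termination visit to assess the local tolerability during the last week".

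The scale is fixed for the assessment: "The assessment will be done using the 4-point scale shown in Panel 15". Panel 15 is titled "Subject assessment of local tolerability after IMP application". It has four grades, 0 to 3, of which 0 reads "No stinging or burning". It has no category for a week in which IMP was not used.

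For timing, Section 10.3 asks subjects who discontinue IMP to attend an "early termination visit as soon as possible after last administration of IMP and return to the trial site for 2 additional visits". Panel 2 (Section 4) shows a dash in the visit-window row for early termination, where the other post-baseline scheduled visits have ±3 days. Section 10.2 rules out restarting IMP.

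Section 11.3 says that the daily compliance item and the weekly tolerability item "will be evaluated by the subject in the eDiary from baseline up to end of treatment/early termination". The visit rating goes into the eCRF (Section 11.5.5, reporting paragraph). The analysis is one sentence in Section 14.3.12.4: "Assessment of local tolerability will be summarised by visit and treatment group".

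**The concern.** The item is meant to measure stinging or burning caused by applying the cream. For a subject who completes treatment, the last application is at home before the Week 16 visit, so the recall week is a week on treatment. For a subject who stops early, the recall week is counted back from a visit whose distance from the last application is not limited. Once that distance reaches a week, question and exposure no longer overlap, and the plan does not say how the subject should answer or how the answer should be handled.

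The mismatch falls only on early discontinuers, who may include those who stopped because of local reactions. Section 5.5 names burning and stinging among the local skin reactions that may occur. What is at stake is the meaning of the early termination values in a descriptive safety table, and of any eDiary values given after IMP was stopped.

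**Working it through.** The plan gives no figure on this point, so there is nothing to reproduce. The check sets the provisions side by side and adds simple arithmetic.

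**1. Overlap of recall week and treatment.** Take the recall week as the 7 days ending on the visit day, and suppose IMP was applied every day until it was stopped.

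Days with IMP in the recall week = max(0, 7 − d), where d is the number of days from last application to visit.

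| d (days) | Days with IMP in recall week |
|---|---|
| 0 | 7 |
| 3 | 4 |
| 6 | 1 |
| 7 or more | 0 |

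Example: last application on Day 20, early termination visit on Day 28. Then d = 8, the recall week is Days 22 to 28, and max(0, 7 − 8) = 0 days with IMP. If the visit day itself is not counted, the threshold moves from 7 to 8 days and the point is unchanged.

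**2. Does the protocol allow d of 7 or more?** Yes. Section 10.3 and Panel 2, footnote 2, ask for the visit as soon as possible and set no upper limit. A delay of this length is also plausible. Scheduled visits fall at Weeks 1, 2, 4, 8, 12 and 16, so from Week 4 they are four weeks apart. Section 9.8.4 places the investigator's review of compliance data before each visit. Section 11.3 does have site staff review eDiary completion throughout the trial, which could shorten the delay. The documents give no distribution of d.

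**3. What can the subject answer?** Panel 15 offers grades 0 to 3 only. With no application in the week, the entry could be 0, a higher grade for residual or disease-related burning, or a grade recalled from earlier applications. The documents do not choose between these, and none is a defined rating of the last week on treatment.

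**4. Is the value removed later?** No. It is recorded in the eCRF and summarised by visit and treatment group. Section 14.3.14 uses observed cases for by-visit tables, so every subject attending the visit counts.

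**5. Does the eDiary item share the problem?** Only conditionally. It is worded in connection with IMP application, but it runs up to end of treatment/early termination. If that means the early termination visit rather than the day treatment stops, a weekly prompt can fall in a week without IMP.

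**6. How many subjects?** With 450 randomised 2:1 (Section 14.1), the arms are 300 and 150. Neither the discontinuation share D nor the share f of early termination visits with d of 7 or more is in the documents. Both are assumed here, and every discontinuing subject is taken to attend the visit.

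Affected subjects = arm size × D × f.

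| D | f | Delgocitinib (300) | Vehicle (150) |
|---|---|---|---|
| 5% | 10% | 1.5 | 0.8 |
| 10% | 25% | 7.5 | 3.8 |
| 20% | 50% | 30.0 | 15.0 |

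Completers seen at Week 16 are not affected.

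**The case against.** The strongest defence is context. The visit question directly follows the eDiary item, which is tied to IMP application, and it uses a scale whose title refers to application. An investigator asking in person could treat it as the same item and point the subject to the last days of use. The end-of-treatment form, with the date of last application, is completed at the same visit, and the actual eCRF and eDiary wording is not in the documents. This makes a sensible reading possible. It does not move the stated recall period, and sites may resolve the ambiguity differently.

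The second defence is that intolerance is captured elsewhere, and this stands:

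- weekly eDiary ratings cover the weeks on treatment;
- the investigator assesses local tolerability at the early termination visit, with scoring and an IMP patch test if a reaction is suspected (Sections 11.5.5 and 11.5.5.1);
- subject-reported tolerability is queried and reported as an AE if deemed relevant (Section 13.2);
- an AE that leads to discontinuation is linked to it (Section 10.2), then tabulated and listed (Section 14.3.12.1).

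For stops due to rescue treatment, Section 9.5 also asks for efficacy and safety assessments immediately before rescue is given, which should shorten the delay for those subjects.

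A reader might infer more than the text supports:

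- **That late subjects will score 0.** Nothing says so; the other answers in step 3 of the working are equally open.
- **That the arms are pulled together.** This would need a difference in stinging between the arms' early discontinuers, and the documents give none.
- **That a low early termination grade contradicts a higher diary grade.** The two may describe different weeks, so both can be true.
- **That intolerance is hidden.** The routes listed above rule this out.

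**Conclusion.** The point holds as a minor measurement defect. The stated recall period covers the wrong week for any early termination visit 7 or more days after the last application, the plan allows such visits, and nothing in the scale or the analysis separates those ratings. For the eDiary item the defect depends on whether prompts continue after IMP is stopped.

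Its reach is the descriptive tolerability summary for early discontinuers. It affects no confirmatory endpoint, and neither the size nor the direction of an effect on the between-arm comparison can be stated from the documents. The counts in the working rest entirely on the assumed discontinuation and delay shares and show only the order of magnitude. Because the information on treatment is collected by other routes, the case for acting is that the table would mean what its title says, at little cost.

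**What to change.** **Section 11.5.5.** Word the early termination item as the worst stinging/burning in connection with IMP application during the 7 days up to and including the last application.

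**Section 14.3.12.4 or the SAP.** Using the date of last application already recorded on the end-of-treatment form (Section 11.8), leave out of the denominator, or show separately, any subject rating whose recall week contains no IMP application. With the convention used above, these are ratings dated 7 or more days after the last application. The rule covers eDiary ratings given after stopping and any early termination ratings collected under the present wording.

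The eDiary item should not be made conditional on the daily question about applying the cream. A missed compliance entry would then suppress a genuine rating.

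**Cost.** One wording change and one derivation rule from data already collected. The downside is slightly older recall when the early termination visit is late. If the wording can no longer be changed, the analysis rule alone can go into the SAP, which Section 14.3.14 says is finalised before the randomisation code is broken.
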